9.4. Human Immunodeficiency Virus Testing and Vaccine Induced Seropositivity

9.4.1. HIV Testing

HIV testing will be performed as indicated in the TIME AND EVENTS SCHEDULE.

At screening of the main study and baseline, subjects will be tested for HIV infection, and must be negative to be entered into the study. If possible, an assay that is US FDA-approved should be selected.

At all other main study visits that include HIV-testing, a study-specific HIV-testing algorithm (detailed in the Laboratory Manual) will be followed. Information provided to the clinical staff of the study site will not include the results of specific tests, but will state only the final interpretation as "HIV infected" or "HIV uninfected". This system allows timely HIV testing without compromising the double-blind nature of the study. The algorithm used for HIV testing throughout the main study aims to differentiate VISP from true HIV infection (see Section 9.4.3).

During the LTE phase, the study-specific HIV-testing algorithm described above will be followed as long as treatment assignment is blinded. Upon study unblinding (after the week 72 database lock), unblinded HIV and VISP results will be reported.

At screening for the late boost vaccination and all subsequent visits of the TIME AND EVENTS SCHEDULE FOR THE LATE BOOST EXTENSIONTIME AND EVENTS SCHEDULE FOR THE LATE BOOST, the study-specific HIV-testing algorithm as described above for the main study will be followed. Information provided to the clinical staff of the study site will not include the results of specific tests, but will state only the final interpretation as "HIV infected" or "HIV uninfected".

9.4.2. Management of Subjects who Become HIV-infected During the Study

Test results performed to confirm the diagnosis will be forwarded to the study staff. Subjects who become HIV infected during the study, including the LTE phase, will be (see Section 12.3.3.1):

- Excluded from further vaccinations.
- Provided counseling and referred for medical treatment.
- Informed about observational studies monitoring subjects with HIV infection.
- Excluded from initiation of the LTE phase.

9.4.3. VISP

In general, HIV-uninfected subjects who participate in preventative HIV-vaccine studies may develop HIV-specific antibodies as a result of an immune response to the candidate HIV vaccine, referred to as VISP. These antibodies may be detected in common HIV-serologic tests, causing the test to appear positive even in the absence of actual HIV infection. Vaccine Induced Seropositivity may become evident during the study or after the study has been completed.

Should an HIV-Ab test give a positive result for a particular subject during the study, the central lab will carry out a follow-up testing algorithm either to exclude or confirm HIV infection. Further details of this algorithm are given in the Laboratory Manual.

To avoid possible unblinding as a result of positive HIV testing due to VISP, subjects should not donate blood during the study. Blood donation options for those subjects who wish to resume blood donation after the study will be explained at the final study follow-up visit.

In the case of VISP, if, either during the study or after the end of the study, a subject requires an HIV test outside the study (eg, to obtain a travel visa or insurance, or for medical reasons), he/she should contact the research center. The center can issue a written statement giving details on VISP and on the testing algorithm to be followed. If requested by a subject, repeat HIV testing will be available at most every 3 months to confirm their HIV status. It is highly preferable that this repeat HIV testing will be performed through the research center. More frequent testing is only allowed after sponsor approval. Testing for a particular subject will be available as long as VISP is present for this subject.

Depending on the local availability of a follow-up protocol, subjects could join into such a study that specifically follows the course of VISP. Such a study may not be available at all sites. However, if such a study is not available, HIV testing will be provided on request as described in the previous paragraph.

In addition to providing testing, subjects will always receive pre- and post-test HIV counseling.

9.4.4. Social Impact

Subjects in preventive HIV-vaccine clinical studies may experience problems with personal relationships, employment, education, health care, housing, health, disability or life insurance, travel, and immigration. In relation to a subject's family, friends, and/or colleagues, the social impact could manifest in one or more ways, resulting in social conflicts and stigmatization:

- 1. The investigational vaccine is thought to be harmful to the subject's health, including a belief that it might cause HIV infection.
- 2. The subject is perceived as HIV infected or at high risk.
- 3. Repercussions from any VISP.

For these reasons, subjects will complete a social impact questionnaire (Attachment 4; at the time points specified in the TIME AND EVENTS SCHEDULE) to evaluate any potential consequences of the subject's participation. For more information, please refer to the Study Procedures Manual.

9.5. Sample Collection and Handling

The actual dates and times of sample collection must be recorded in the CRF or laboratory requisition form.

See the TIME AND EVENTS SCHEDULE for the timing and frequency of all sample collections.

Instructions for the collection, handling, storage, and shipment of samples are found in the Study Procedures Manual that will be provided. Collection, handling, storage, and shipment of samples must be under the specified, and where applicable, controlled temperature conditions as indicated in the Laboratory Manual.

10. SUBJECT COMPLETION/DISCONTINUATION OF STUDY TREATMENT/ WITHDRAWAL FROM THE STUDY

10.1. Completion

A subject who is not participating in the LTE phase will be considered to have completed the study if he or she has completed the assessments at Week 72.

A subject who is participating in the LTE phase will be considered to have completed the main study if he or she has completed the assessments at Week 72 and will be considered to have completed the LTE phase if he or she has completed the assessments at the last visit of the LTE phase (Week 216).

Subjects receiving the late boost vaccination will have completed the study if he or she has completed the assessments at Week 240, if opting for 12 months of follow-up post-boost, or Week 288, if opting for 24 months of follow-up post-late boost.

10.2. Discontinuation of Study Treatment/Withdrawal from the Study

Discontinuation of Study Treatment

Subjects will be withdrawn from study vaccine administration during the main study for the reasons listed below. These subjects must not receive any additional dose of study vaccine but should enter the follow-up phase with assessments of safety and immunogenicity. The subject will be encouraged to complete the post-vaccination follow-up visits of the last vaccination received and a 12 and 24 weeks follow-up visit after the last vaccination received, specified as Week 60 and Week 72 in the TIME AND EVENTS SCHEDULE. Additional unscheduled visits may be performed for safety/tolerability reasons, if needed. In case the subject withdraws before receiving the first vaccination, the subject is not required to attend follow-up visits. In case of questions, the investigator is encouraged to contact the study responsible physician. Subjects who have been prematurely withdrawn from study vaccine administration are not eligible for the LTE phase.

- Unblinding
- Anaphylactic reaction following vaccination
- Pregnancy
- Any related SAE
- Any related AE, worsening of health status or intercurrent illnesses that, in the opinion of the investigator, requires discontinuation from study vaccine
- Confirmed HIV infection
- Chronic or recurrent use of immunosuppressants (after discussion with the sponsor)

• Missing more than 1 study vaccination

Withdrawal From the Study

Each subject has the right to withdraw from the study at any time for any reason without affecting the right to treatment by the investigator. The investigator should make an attempt to contact subjects who did not return for scheduled visits or follow-up. Although the subject is not obliged to give reason(s) for withdrawing prematurely, the investigator should make a reasonable effort to ascertain the reason(s) while fully respecting the subject's rights.

A subject will be withdrawn from the study for any of the following reasons:

- Lost to follow-up
- Withdrawal of consent
- Death
- Repeated failure to comply with protocol requirements
- Decision by the sponsor or the investigator to stop or cancel the study
- Decision by local regulatory authorities or IRB/IEC to stop or cancel the study

If a subject is lost to follow-up, every reasonable effort (at least 2 documented attempts to contact the subject by telephone and at least one documented written attempt) must be made by the study-site personnel to contact the subject and determine the reason for discontinuation/withdrawal. The measures taken to follow-up must be documented.

When a subject withdraws before completing the study, the reason for withdrawal is to be documented in the CRF and in the source document. Study vaccine assigned to the withdrawn subject may not be assigned to another subject. Subjects who are vaccinated and who withdraw will not be replaced. If a subject withdraws early from the study, assessments for early withdrawal should be obtained (see Section 9.1.7).

Subjects who wish to withdraw consent from participation in the study will be offered a single Exit visit for safety follow-up (prior to formal withdrawal of consent). They have the right to refuse. The exit visit is only applicable to the main study until Week 72 and for subjects who received the late boost vaccination.

A subject who withdraws from the study will have the following options regarding the use of optional research samples which were collected:

- The collected samples will be retained and used in accordance with the subject's original informed consent appendix for optional research samples.
- The subject may withdraw consent for optional research samples, in which case the samples will be destroyed and no further testing will take place. To initiate the sample destruction process, the investigator must notify the sponsor study site contact of withdrawal of consent

for the optional research samples and to request sample destruction. If requested, the investigator will receive written confirmation from the sponsor that the samples have been destroyed.

10.3. Contraindications to Vaccination

The following events constitute a contraindication to vaccination at that point in time. If any of these events occur at the scheduled time for vaccination, the vaccination can be rescheduled (as long as this is in agreement with the allowed windows, see Section 9.1.2):

- Acute illness at the time of vaccination. This does not include minor illnesses, such as diarrhea or mild upper-respiratory tract infection.
- Fever (oral temperature $\ge 38.0^{\circ}$ C) at the planned time of vaccination.

10.4. Withdrawal From the Use of Samples in Future Research

The subject may withdraw consent for use of samples for research (refer to Section 16.2.5, Long-term Retention of Samples for Additional Future Research). In such a case, samples will be destroyed after they are no longer needed for the clinical study. Details of the sample retention for research are presented in the ICF.

11. STATISTICAL METHODS

Statistical analysis will be done by the sponsor or under the authority of the sponsor. A general description of the statistical methods to be used to analyze the safety and immunogenicity data is outlined below. Specific details will be provided in the Statistical Analysis Plan.

11.1. Subject Information

For all subjects, demographic characteristics (eg, age, height, weight, body mass index [BMI], race, and gender), and other baseline characteristics (eg, medical history, concomitant diseases) will be tabulated and summarized with descriptive statistics.

11.2. Analysis Populations

The safety population will consist of all subjects who received at least one dose of study vaccine, and for whom any post-dose data is available.

The immunogenicity population will consist of all subjects who received at least one dose of study vaccine, and who have immunogenicity data from at least one evaluable post-dose blood sample.

The per protocol immunogenicity population will consist of all randomized and vaccinated subjects for whom immunogenicity data are available, excluding subject samples with major protocol deviations expecting to impact the immunogenicity outcomes (for example missed vaccinations, natural infections, etc).

11.3. Sample Size Determination

The sample size in this study is regarded to be appropriate to assess the safety and tolerability of the different vaccine regimens. Placebo recipients are included for blinding and safety purposes and will provide control specimens for immunogenicity assays. With 25 individuals in a vaccine regimen, the observation of 0 such reactions would be associated with a 95% confidence that the true rate is less than 12%. For Group 2 with Mosaic and Clade C gp140 (n=100), there would be 95% confidence that the true rate is less than 3% when 0 events are observed. The following table shows the probabilities of observing at least one AE given true AE rates.

Probability of Observing at Least One AE in n Subjects

True AE Rate	n = 25	n = 100
0.1%	2%	9.5%
0.5%	12%	39%
1.0%	22%	63%
2.5%	47%	92%
5.0%	72%	99%
10.0%	93%	100%

The primary population for the safety analyses will consist of all subjects who received at least 1 dose (Ad26.Mos4.HIV or placebo).

Anticipating a dropout rate of approximately 10%, the sample sizes will allow detection of approximately 1.85-fold differences in Env-binding Ab titers, generally accepted to be biologically relevant, between the groups with Mosaic and Clade C gp140 (approximately 90 evaluable subjects) and their corresponding group with Clade C gp140 only (approximately 22 evaluable subjects); with 80% probability, assuming a 2-sided 5% Type I error and an SD of 0.4 on the log₁₀ scale.

11.4. Immunogenicity Analyses

Descriptive statistics (actual values and changes from reference) will be calculated for continuous parameters. Frequency tabulations will be calculated for discrete parameters. Graphical representations of changes in immunologic parameters will be made as applicable.

No formal hypothesis on immunogenicity will be tested. The analysis of immunogenicity will be done on the (per protocol) immunogenicity population as defined in Section 11.2.

Breadth of the binding Ab response will be summarized as the number of HIV clades to which a subject shows an Ab response. Magnitude and breadth of (n)Ab responses will be explored graphically through the generation of individual magnitude-breadth (M-B) curves. The area under the M-B curve (AUC) provides an overall summary of the M-B profile. The AUCs will be compared between groups using the Wilcoxon-Mann-Whitney test.

Differences between groups at a specific time point will be tested for exploratory purposes by a 2-sample t-test if the data appear to be normally distributed. If not, the non-parametric Wilcoxon rank sum test will be used. If portions of the measurements are censored below the assay

quantification limit, the Gehan-Wilcoxon test will be employed. All statistical tests will be 2-sided and will be considered statistically significant if p<0.05.

Frequency tabulations will be calculated for discrete (qualitative) immunologic parameters. Significant differences between groups will be determined by a 2-sided Fisher's exact test.

11.5. Safety Analyses

No formal statistical testing of safety data is planned. Safety data will be analyzed descriptively.

Baseline for all safety parameters will be defined as the last evaluation done before the first dose of study vaccine.

AEs

The verbatim terms used in the CRF by investigators to identify AEs will be coded using the Medical Dictionary for Regulatory Activities (MedDRA). All reported AEs and events-related diary information (solicited local at injection site and systemic, and unsolicited) with onset within 28 days after vaccination (ie, treatment-emergent AEs, and AEs that have worsened since baseline) will be included in the analysis. For each adverse event, the percentage of subjects who experience at least 1 occurrence of the given event will be summarized by vaccine group.

Treatment-emergent AEs are AEs with onset during the treatment phase or that are a consequence of a pre-existing condition that has worsened since baseline. All reported AEs will be included in the analysis. For each AE, the percentage of subjects who experience at least 1 occurrence of the given event will be summarized by treatment group. In addition, comparisons between treatment groups will be provided if appropriate.

Summaries, listings, datasets, or subject narratives may be provided, as appropriate, for those subjects who die, who discontinue treatment due to an adverse event, who experience a severe or a serious AE or an AESI.

Summaries and listings may be provided separately for AEs with onset outside the above defined timeframe and that were reported pre-dose at the moment of subsequent vaccinations.

Solicited local (at injection site) and systemic AEs will be summarized descriptively. The overall frequencies per vaccine group as well as frequencies according to severity and duration will be calculated for solicited AEs. In addition, the number and percentages of subjects with at least one solicited local (at injection site) or systemic AE will be presented. Frequencies of solicited and unsolicited AEs, separately for all and vaccination-related only, will be presented by System Organ Class and preferred term.

Clinical Laboratory Tests

Laboratory data will be summarized by type of laboratory test. Laboratory abnormalities will be determined according to a modified version of the DAIDS grading table, Version 2.0 (Attachment 1), and in accordance with the normal ranges of the clinical laboratory. Laboratory abnormalities will be tabulated per vaccine group and/or treatment group.

Vital Signs

The percentage of subjects with values beyond pre-specified limits (see Attachment 1) will be summarized.

Physical Examination

Physical examination findings will not be tabulated separately. Clinically relevant findings will be reported as AE and will be tabulated and listed as AEs. BMI will be calculated using the recording of height at screening.

Social Impact Questionnaire

Data from the Social Impact Questionnaire will be summarized using descriptive statistics.

Vector Shedding Analyses

Vector shedding data will be analyzed descriptively.

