PARAMETER	GRADE 1 MILD	GRADE 2 MODERATE	GRADE 3 SEVERE	GRADE 4 POTENTIALLY LIFE- THREATENING
Clinical adverse event NOT identified elsewhere in the grading table	Mild symptoms causing no or minimal interference with usual social & functional activities with intervention not indicated	Moderate symptoms causing greater than minimal interference with usual social & functional activities with intervention indicated	Severe symptoms causing inability to perform usual social & functional activities with intervention or hospitalization indicated	Potentially life- threatening symptoms causing inability to perform basic self-care functions with intervention indicated to prevent permanent impairment, persistent disability, or death

MAJOR CLINICAL CONDITIONS				
	,	CARDIOVASCULAR	10110	
PARAMETER	GRADE 1 MILD	GRADE 2 MODERATE	GRADE 3 SEVERE	GRADE 4 POTENTIALLY LIFE- THREATENING
Arrhythmia (by ECG or physical examination) Specify type, if applicable	No symptoms AND No intervention indicated	No symptoms AND Non-urgent intervention indicated	Non-life-threatening symptoms AND Non- urgent intervention indicated	Life-threatening arrhythmia OR Urgent intervention indicated
Blood Pressure Abnormalities ¹ Hypertension (with	140 to <160 mmHg	≥160 to <180 mmHg	≥180 mmHg systolic	Life-threatening
the lowest reading taken after repeat testing during a visit) ≥18 years of age	systolic OR 90 to <100 mmHg diastolic	systolic OR ≥100 to <110 mmHg diastolic	OR ≥110 mmHg diastolic	consequences in a participant not previously diagnosed with hypertension (eg. malignant hypertension) OR Hospitalization indicated
<18 years of age	>120/80 mmHg	≥95th to <99th percentile + 5 mmHg adjusted for age, height, and gender (systolic and/or diastolic)	≥99th percentile + 5 mmHg adjusted for age, height, and gender (systolic and/or diastolic)	Life-threatening consequences in a participant not previously diagnosed with hypertension (eg, malignant hypertension) OR Hospitalization indicated
Hypotension	No symptoms	Symptoms corrected with oral fluid replacement	Symptoms AND IV fluids indicated	Shock requiring use of vasopressors or mechanical assistance to maintain blood pressure
Tachycardiaº - beats per minute	101 - 115	116 - 130	> 130	ER visit or hospitalization for arrhythmia
Bradycardia ^a - beats per minute	50 - 54	45 - 49	< 45	ER visit or hospitalization for arrhythmia

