Fever (non-axillary temperatures only)	38.0 to <38.6°C or 100.4 to <101.5°F	≥38.6 to <39.3°C or ≥101.5 to <102.7°F	≥39.3 to <40.0°C or ≥102.7 to <104.0°F	≥40.0°C or ≥104.0°F
Pain ¹⁰ (not associated with study agent injections and not specified elsewhere) Specify location	Pain causing no or minimal interference with usual social & functional activities	Pain causing greater than minimal interference with usual social & functional activities	Pain causing inability to perform usual social & functional activities	Disabling pain causing inability to perform basic self-care functions OR Hospitalization indicated
Serum Sickness ¹¹	Mild signs and symptoms	Moderate signs and symptoms AND Intervention indicated (eg, antihistamines)	Severe signs and symptoms AND Higher level intervention indicated (eg, steroids or IV fluids)	Life-threatening consequences (eg, requiring pressor or ventilator support)
Underweight ¹² >5 to 19 years of age	NA	WHO BMI z-score <-2 to ≤-3	WHO BMI z-score <-3	WHO BMI z-score <-3 with life-threatening consequences
2 to 5 years of age	NA	WHO Weight-for- height z-score <-2 to ≤-3	WHO Weight-for- height z-score <-3	WHO Weight-for- height z-score <-3 with life-threatening consequences
<2 years of age 9 Definition: A disorder char	NA	WHO Weight-for- length z-score <-2 to ≤-3	WHO Weight-for- length z-score <-3	WHO Weight-for- length z-score <-3 with life-threatening consequences

⁹ Definition: A disorder characterized by nausea, headache, tachycardia, hypotension, rash, and/or shortness of breath.

http://www.who.int/childgrowth/standards/chart catalogue/en/ for those ≤5 years of age.

¹⁰ For pain associated with injections or infusions, see the *Site Reactions to Injections and Infusions* section.

¹¹ Definition: A disorder characterized by fever, arthralgia, myalgia, skin eruptions, lymphadenopathy, marked discomfort, and/or dyspnea.

¹² WHO reference tables may be accessed by clicking the desired age range or by accessing the following URLs: http://www.who.int/growthref/who2007 bmi for age/en/ for participants >5 to 19 years of age and

JNJ-55471468, JNJ-55471494, JNJ-55471520, JNJ-55471585, JNJ-64219324, JNJ-64219311, JNJ-65184340 Clinical Protocol Amendment 6

PARAMETER	GRADE 1	GRADE 2	GRADE 3	GRADE 4
	MILD	MODERATE	SEVERE	POTENTIALLY
				LIFE-
				THREATENING

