## 5.2. Clinical Laboratory Tests

Any clinically relevant lab value measured from signing of the ICF onwards must be recorded on the adverse event page of the CRF and are analyzed as AE. The data will be summarized by the type of laboratory test.

In case a laboratory test result is *censored* (no numeric value is available, but only a verbatim term) then a numeric value will be imputed by a value preceding or exceeding the cut-off value with one unit. (<x: subtract 1 unit from x, >x: add 1 unit to x)

*Toxicity grades* will be determined according to the DAIDS Grading list (See also Appendix 1). In case no toxicity grades are defined for a test, the abnormalities (above/below normal range) will be used. In determining toxicity grades, the following rules are applied:

- worst grades/abnormalities are determined over the whole observational period for each trial phase separately, including all post-baseline measurements of that phase.
- The abnormalities ‘abnormally low’ and ‘abnormally high’ are considered equally important, i.e. if a subject has as well an abnormally low as an abnormally high value post-baseline, both abnormalities are shown in the tables. (This means that the sum of the percentages can be more than 100%)
- Note: as the grading scale for some parameters in the grading table has some gaps (zones where no toxicity grade definition exists), laboratory results falling in these zones will be allocated to the adjacent worst-case grade.
- If a lab value falls within the grading as specified in the grading table but also within the (local) lab normal limits, the value is considered as normal

***Definition emergent:*** An abnormality (toxicity grade or abnormality based on normal ranges) will be considered emergent in a particular phase if it is worse than the baseline (baseline = prior very first vaccination). If the baseline is missing, the abnormality is always considered as emergent. A shift from ‘abnormally low’ at baseline to ‘abnormally high’ post baseline (or vice versa) is also emergent.

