### 5.3. Vital Signs

#### 5.3.1. Definitions

Vital sign measurements will be performed at the time points indicated in the Time and Events Schedule (see CTP). Following parameters will be summarized:

- Temperature (°C)
- Blood Pressure: systolic/diastolic (mmHg)
- Pulse rate (bpm)

For definition of emergent refer to section 5.2.

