#### 5.3.2. Analysis methodology

Any clinically relevant vital signs occurring from signing of the ICF onwards must be recorded on the adverse event page of the CRF and are analyzed as AEs. Tabulations of the parameters per period following vaccination will be provided. All findings will be listed by subject and by time point. Tabulations of the worst emerging abnormalities will be performed for parameters if applicable (see grading on Appendix 1).

Physical examination data will be listed.

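### The vital-sign limits printed in SAP Appendix 1 differ from protocol Attachment 1 and leave twelve gradable readings with no grade

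*Protocol*

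**What the plan says.** Protocol section 11.5 (Vital Signs) makes Attachment 1 the yardstick: "The percentage of subjects with values beyond pre-specified limits (see Attachment 1) will be summarized". The bands in Attachment 1 meet without gaps at the precision at which vital signs are normally recorded. Fever Grade 3 is "≥39.3 to <40.0°C or ≥102.7 to <104.0°F", systolic Grade 2 is "≥160 to <180 mmHg", and the Grade 1 entry for hypertension reads "systolic OR 90 to <100 mmHg diastolic" for its diastolic part. The pulse bands are closed whole-number ranges: 101 to 115 and 116 to 130 for tachycardia, 50 to 54 and 45 to 49 for bradycardia.

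SAP section 5.3.2 says: "Tabulations of the worst emerging abnormalities will be performed for parameters if applicable (see grading on Appendix 1"). The vital-signs table in SAP Appendix 1 carries a footnote that identifies it as DAIDS 2.0 grading and points to the protocol's grading table. Its bands nevertheless put a strict less-than sign in front of the last value that belongs to each band: below 38.5, 39.2 and 39.9 °C; below 159 and 179 systolic; below 99 and 109 diastolic; below 115, 130, 54 and 49 bpm. It also starts diastolic Grade 1 strictly above 90.

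The SAP has one rule for values that fall between grades. It is in section 5.2 (Clinical Laboratory Tests) and says that "laboratory results falling in these zones will be allocated to the adjacent worst-case grade". The vital-signs section takes one thing from 5.2: "For definition of emergent refer to section 5.2".

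**The concern.** The SAP table presents itself as a copy of the protocol grading, and its limits are not a copy. A value at the top of a band, such as 39.9 °C or a systolic pressure of 179, belongs to a grade under the protocol and to none under the SAP. The SAP does not say what to do with such a vital sign, so two competent programmers could treat it differently, and neither treatment would match the protocol.

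What is at stake is the accuracy of the vital-sign abnormality tables. Safety and tolerability are primary objectives, and the protocol analyses safety descriptively, so these counts are reported as they stand.

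**Working it through.** There is no planned figure to reproduce. The check grades every reading under both sets of limits.

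**Inputs.** Limits from protocol Attachment 1 (cardiovascular and systemic parts) and from the vital-signs table of SAP Appendix 1. Precision is assumed: 0.1 °C, whole mmHg, whole bpm.

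**Step 1. Readings graded by Attachment 1 but not by the SAP.** The last column shows the grade if the laboratory gap rule of SAP 5.2 were borrowed.

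| Reading | Attachment 1 | SAP as printed | With borrowed rule |
|---|---|---|---|
| 38.5 °C | 1 | none | 2 |
| 39.2 °C | 2 | none | 3 |
| 39.9 °C | 3 | none | 4 |
| Systolic 159 | 1 | none | 2 |
| Systolic 179 | 2 | none | 3 |
| Diastolic 90 | 1 | none | 1 |
| Diastolic 99 | 1 | none | 2 |
| Diastolic 109 | 2 | none | 3 |
| Pulse 115 | 1 | none | 2 |
| Pulse 130 | 2 | none | 3 |
| Pulse 54 | 1 | none | 1 |
| Pulse 49 | 2 | none | 2 |

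All twelve are ungraded as printed. With the borrowed rule, nine are one grade too high and three (diastolic 90, pulse 54 and 49) land correctly. No other reading differs.

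**Step 2. How often this could matter.** The documents give no vital-sign distributions, so the following is illustrative. Assume normal readings rounded to whole units, P(k) = Φ((k+0.5−μ)/σ) − Φ((k−0.5−μ)/σ), with diastolic mean 74-80 and SD 8-10, systolic mean 118-126 and SD 11-14, pulse mean 68-75 and SD 9-11.

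*Lost without the rule* = sum of P(ungraded readings) / P(Grade 1 or above):
- Diastolic, mean 80, SD 10: (2.420% + 0.657% + 0.060%) / 17.106% = 18.3%. At mean 74, SD 8: 27.1%.
- Systolic, mean 126, SD 14: (0.177% + 0.002%) / 16.745% = 1.1%. At mean 118, SD 11: 0.1%.
- Bradycardia: 22% (mean 68, SD 11) to 32% (mean 75, SD 9).

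*Shown as Grade 2 or above with the rule, but Grade 1 under Attachment 1*:
- Diastolic = P(99) / P(99 or more): 0.657% / 3.216% = 20.4% (mean 80, SD 10), up to 35% (mean 74, SD 8).
- Systolic = P(159) / P(159 or more): 0.177% / 1.013% = 17.5% (mean 126, SD 14), up to 30% (mean 118, SD 11).

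**Step 3. Absolute size.** The second pair of shares comes from a thin tail. P(99 diastolic) is 0.04-0.66% of readings and P(159 systolic) 0.004-0.18%. With one reading each from 48 subjects, the late-boost enrolment target, that is 48 × 0.0004 to 48 × 0.0066, about 0.02 to 0.3 readings, and 48 × 0.00004 to 48 × 0.0018, about 0.002 to 0.09.

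**The case against.** The strongest reply is that the signs may be an artefact of reading the PDF. If each upper limit was really less-than-or-equal, every upper limit would match Attachment 1 at recorded precision, and the lone strict lower limit at diastolic 90 could be a lost bar. The laboratory rows of the same appendix print inclusive last values, which fits. This cannot be excluded, which is why the fix starts with the source file. But greater-than-or-equal signs survive in the same rows, and the text as supplied is strict throughout the upper limits.

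Second, the footnote points to the protocol table, and protocol 11.5 names Attachment 1. A programmer who follows either grades all twelve readings correctly. That stands, and it rules out a tempting stronger reading, that every way of applying the SAP gives wrong tables. The footnote shows the intent; it does not correct the printed limits that 5.3.2 tells the analyst to use.

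Third, a reader might infer that a systolic pressure of 179 will be reported as normal, or that 39.9 °C will appear as Grade 4. The SAP states neither. The first is inferred from a reading having no grade. The second needs a rule that names laboratory results only.

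Fourth, a reader might infer that one temperature will carry two grades, or that safety oversight is weakened. The documents do not support this. Solicited fever in the tables comes from the diary pages and, where no grade is available, is graded by Attachment 1 (SAP 5.1.1), whereas vital-sign temperature is a clinic measurement. Adverse events are graded by Attachment 1 (protocol 12.1.3), clinically relevant vital signs are recorded and analysed as adverse events, all vital-sign findings are listed (SAP 5.3.2), and the holding rules in protocol 11.9 act on adverse events.

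**Conclusion.** The point holds for the SAP as supplied. The defect is in the vital-signs table of SAP Appendix 1; the protocol sentence is the correct standard from which it departs. The twelve-reading result depends only on the printed limits and the assumed recording precision. The percentages depend on assumed means and SDs, and are shares of readings, whereas protocol 11.5 summarises subjects and SAP 5.3.2 tabulates the worst emerging value.

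Within those assumptions the loss is material for diastolic pressure and bradycardia and negligible for systolic pressure. The upgrade under a borrowed gap rule is a large share of very few readings.

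The forward scope is narrow. The SAP introduction says that outputs up to Week 72 will not be repeated. The long-term extension schedule has no vital signs, and the late-boost schedule takes them only at screening, before and after the dose, and at an exit visit. The documents do not show whether earlier tables were programmed with the printed limits. This should be corrected, but it does not threaten the trial's conclusions.

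**What to change.** Check the inequality signs in the source SAP. Then make the vital-sign limits in Appendix 1 identical to Attachment 1:

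- Temperature (°C): 38.0 to <38.6; 38.6 to <39.3; 39.3 to <40.0; ≥40.0.
- Systolic (mmHg): 140 to <160; 160 to <180; ≥180.
- Diastolic (mmHg): 90 to <100; 100 to <110; ≥110.
- Tachycardia (bpm): 101-115; 116-130; >130.
- Bradycardia (bpm): 50-54; 45-49; <45.

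With these limits no reading at the assumed precision falls between grades, so vital signs need no gap rule; one sentence in SAP 5.3 can say so. Apply the limits to the late-boost outputs. Re-run earlier vital-sign tables only if the programs used the printed SAP limits. The cost is a table edit and a small programming change, with no new data.
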